Quantitative data series are available for London on use of transport, including walking and cycling (London Area Travel Survey (LATS), London Travel Demand Survey (LTDS)), and injuries (Stats19 road injury data, Hospital Episode Statistics (HES)). These allow analyses of change in important outcomes following the introduction of the free bus and tram travel scheme. The quantification of change will be based on before-after comparisons using two time points: (i) the introduction of free bus travel in London to children <16 years in September 2005 and (ii) its extension to those under 18 years in September 2006. To minimize possible bias arising from changes over time in the completeness of data recording, for most analyses we propose to compare the changes in the relevant outcomes in the under 18s (under 16s) with those observed at other ages: a *change-on-change* analysis. Although this carries some penalty in terms of statistical power, the comparatively large number of events at other ages means the penalty is modest, while achieving a gain of reduced potential for bias. We will examine the following outcomes:

- the frequency and distance of active transport (i.e. walking and cycling) in those aged 12–17 years;
- the frequency of **bus use and the distance travelled by bus**, in those aged 12–15 and 16–17 years;
- the frequency of bus travel and the distance travelled by bus in other age groups;
- the **incidence of intentional and non-intentional injuries** in young people aged 12-17.

Table 1: Available sample sizes of main secondary data sets

Table 1. Available	Sample	31203 01	main sc	, con luar y	uala se	,10			
	2001	2002	2003	2004	2005	2006	2007	2008	
FREE BUS/TRAM					<16s	<18s			
SCHEME									
		Pre-inte	rvention		Post-intervention periods				
London Area									
Travel									
Survey	30,000								
(LATS)	30,000								
[number of									
households]									
London Travel &									
Demand Survey					5,000	8,000	8,000	8,000	
(LTDS) [number of					3,000	8,000	8,000	8,000	
households]									
National Travel									
Surveys (NTS)	9,000	9,000	9,000	9,000	9,000	9,000	9,000		
[number of	3,000					3,000	3,000		
households]									
Stats19 [persons]	45,000	41,000	39,000	35,000	32,000	29,000	Not yet	Not yet	
(percent in 12-17	(7%)	(7%)	(7%)	(7%)	(7%)	(6%)	analysed	analysed	
years)									
Hospital Episode	100k	100k	100k	100k	100k	100k	100k	100k	
Statistics	(350)	(350)	(350)	(350)	(350)	(350)	(350)	(350)	
(external cause									

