admissions in									
London)									

Travel patterns: LATS, LTDS. We will use data collected five years before the interventions in the 2001 London Area Transport Survey (LATS), and data from the 2005–2007 London Travel Demand Surveys (LTDS) for the post-interventions period. The LATS and LTDS surveys collect comparable travel data sets based on daily travel diaries, using comparable sampling designs. The 2001 LATS included 30,000 households and LTDS included 5,000 households in 2005, with a further 8,000 households annually since 2006. Every person aged over 5 years living in each household is asked to complete a one-day travel diary that records the starts, interchanges and ends of every trip made on that day. In 2001 LATS there were 360,389 interchanges (parts of trips) made by 67,252 individuals. With similar levels of travel in 2005–2008 we expect data to be available on over 250,000 travel interchanges made by 47,000 individuals. Journey times are collected in both LATS and LTDS. Journey distance is estimated using the start-point, interchange and endpoint of each trip (these locations are geo-coded and 'crow-fly' distances are easily calculated). For the travel patterns, comparisons will also be made with data from the National Travel Survey (NTS, Department for Transport). This national survey includes samples of approximately 9,000 households each year, including

approximately 20,000 individuals, with data from seven day travel diaries for each individual. The inclusion of NTS data will enable us to assess whether trends in main travel modes nationally and in other urban areas differ to those used as main modes in London.

Travel-related injuries and assaults: Stats19, bus incident reports, HES. **STATS19 road injury data,** the official dataset of human death and personal injuries from road traffic crashes on the public highway in the UK, are available for each year of the study (to 2009). We will analyse casualties among young people travelling as pedestrians, cyclists, car occupants and bus occupants, and by severity of injury ('Fatal' or 'Serious' (hospital admission), and 'Slight' - minor injuries).

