Analysis. For all outcomes, the principal analysis will be the comparison of the change before and after September 2005 (for those aged 12-15), and before and after September 2006 (for those aged 16–17 years). These changes will be compared with similarly-defined change at other ages. Where relevant, appropriate denominator populations (ONS population projections) will be used to allow for differences between years in the number of young people at risk. Robust standard errors will be calculated, clustering on borough to allow for similarities of outcome at that geographical level. We will also explore the use of other multi-level modelling methods to allow for other forms of data hierarchy relating to spatial variation in bus service provision.

To assess the impact of the interventions on transport (including active transport) we will compare mean times and distances, as well as the percentage of short distance trips travelled by the relevant mode (walking, cycling, bus, car). We will also estimate changes in amounts of travel on journeys to work or school in people aged under 18 years (to assess potential increased access to education).

For all outcomes, we will investigate evidence for variations by socio-economic group or household income and, where possible, by ethnicity (to address questions of impact on inequalities), although power will be limited for most such sub-group analyses.

Sample size Example of power to detect changes in distance of trips made by bus and walking

Provisional 2001 estimates of the distances of trips made by young people by bus and by walking are shown below. With 3,000 young people in the sample before and after the intervention, the study will have 80% power to detect a 10% reduction in the average daily distances walked by young people (from an average 0.91 km per day to 0.82 km per day) at a 5% significance level. Similarly, the study would have 98% power to detect a 10% increase in the distance of bus travel from an average of 4.33 km per day to an average 4.76 km per day. For transport-related injury, the study would have 80% power to detect a 10% change, or 90% power to detect a 12% change significant at the 5% level. Statistical power is inevitably more limited for subgroup analyses, but for example there is 90% power to detect a 15% change in average distance travelled by bus by young people within the most deprived quartile.

Table 2: Average distances by mode for Londoners aged 12-17 years (LATS 2001)

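### The stated walking and bus power belongs to a simple before-after comparison, not to the planned change-on-change analysis, and at 3,000 v 3,000 the walking figure has no reserve

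*Protocol*

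**What the plan says.** All of this is in protocol section 4.2.3.

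- **Sample size.** The example is set up as "With 3,000 young people in the sample before and after the intervention". For walking it claims that "the study will have 80% power to detect a 10% reduction in the average daily distances walked by young people". The mean is taken to fall from 0.91 to 0.82 km daily, and the test level is 5%. For bus, "the study would have 98% power to detect a 10% increase in the distance of bus travel". No comparison group, intracluster correlation or design effect is mentioned.
- **Analysis.** The principal analysis is the change around September 2005 for ages 12-15 and around September 2006 for ages 16-17, each set against the corresponding change at other ages. "Robust standard errors will be calculated, clustering on borough".
- **Change-on-change.** The introduction to the quantitative analyses concedes a cost: "Although this carries some penalty in terms of statistical power". It calls this cost modest because other ages supply many events.
- **Travel patterns.** The surveys take whole households: "Every person aged over 5 years living in each household is asked to complete a one-day travel diary". LATS 2001 covered 67,252 individuals in 30,000 households. About 47,000 individuals are expected for 2005-2008, although the same paragraph first gives the post-intervention data as LTDS 2005-2007.
- **Table 2.** LATS 2001 held 5,450 people aged 12-17 (3,150 aged 12-15 and 2,300 aged 16-17). Overall SDs are 1.26 km for walking and 4.1 km for bus.

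**The concern.** The power statement and the analysis plan describe different calculations. The power statement is a one-group before-after comparison of independent people. The planned estimate subtracts a second change, measured with its own error, and allows for correlation within boroughs. Siblings in the same household may also travel alike. The protocol acknowledges the first cost and plans for the second, yet neither is in the stated figure.

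This matters mainly for walking. Active transport is a key outcome (section 7), a reduction in it is the stated hypothesis (section 2.2), and the change feeds the economic evaluation (section 4.2.5). If no change in walking is found, readers will judge that result against the claimed 80%, so the figure should belong to the analysis that produced the result.

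**Working it through.** **Inputs from the protocol:** 3,000 before and after; 10% changes of 0.091 km (walking) and 0.433 km (bus); SDs 1.26 and 4.1; 5% level.

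**Assumptions:** two-sided test; normal approximation; the same SD at other ages; all other surveyed ages as comparator, which is the most favourable choice.

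**Formula:** power = Φ(δ/SE − 1.96), with SE = SD × √(D × V). D is the design effect and V the sum of reciprocal group sizes.

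**Step 1. Reproduce the stated figures.** V = 2/3,000 = 0.000667, D = 1.
- Walking: SE = 1.26 × √0.000667 = 0.03253; 0.091/0.03253 = 2.797; power 79.9% (79.0% with the rounded 0.09).
- Bus: SE = 4.1 × √0.000667 = 0.1059; 0.433/0.1059 = 4.090; power 98.3%.

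Both match with no comparator and no clustering.

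**Step 2. Add the comparison with other ages at 3,000 v 3,000.**
- Other ages before: 67,252 − 5,450 = 61,802.
- The 2001 share aged 12-17 is 5,450/67,252 = 8.1%. Applied to 47,000, it gives about 3,809 young people and 43,191 others after.
- Added term: 1/61,802 + 1/43,191 = 0.0000393, which is 5.9% of 0.000667. V = 0.000706.
- Walking at D = 1: SE = 0.03348; 0.091/0.03348 = 2.718; power 77.6%.
- Bus at D = 1: 97.8%.

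The comparison alone costs walking about 2 points.

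**Step 3. Add an assumed design effect at 3,000 v 3,000.** The protocol gives none, so this is a range only.

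| D | Walking | Bus |
|---|---|---|
| 1.0 | 77.6% | 97.8% |
| 1.05 | 75.6% | 97% |
| 1.2 | 69.9% | 95% |
| 1.5 | 60.2% | 90% |

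**Step 4. Use the numbers the protocol describes.** V = 1/5,450 + 1/3,809 + 1/61,802 + 1/43,191 = 0.000485.
- Walking: 90.6% at D = 1, 85% at 1.2, 76% at 1.5.
- Power of 80% needs δ/SE = 2.80, so the largest D that keeps it is (0.091/(1.26 × 2.80))²/0.000485, about 1.37.
- Bus: 99.8% at D = 1, 97.5% at 1.5.

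**Step 5. Count only LTDS 2005-2007.** Table 1 gives 21,000 of the 29,000 LTDS households for those years. Pro rata, that is about 2,758 young people and 31,276 others after; V = 0.000594.
- Walking: 84% at D = 1, 77% at 1.2.
- 80% holds up to D of about 1.12.

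**Step 6. Use the age bands of the principal analysis.** These are 10% walking changes with the band means and SDs of Table 2, the Step 4 comparator and D = 1.
- 12-15: 3,150 before, about 2,201 after; δ = 0.087, SD 1.2; power about 72%.
- 16-17: 2,300 before, about 1,607 after; δ = 0.095, SD 1.35; power about 57%.

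**The case against.** The strongest reply is that the paragraph is headed as an example and uses a round number below the data available. This stands. A reader might infer from the 3,000 v 3,000 results that the design cannot deliver the walking power. The documents do not support that reading, because with the numbers in Step 4 the pooled contrast exceeds 80% unless the design effect passes about 1.37. The reserve is thinner if the post-intervention data stop at 2007.

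The change-on-change penalty is also disclosed, and calling it modest is fair when all other ages are used.

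The size of any clustering loss is not in the documents. The 67,252 people in 30,000 households are of all ages; those aged 12-17 average only 5,450/30,000 = 0.18 per household, and how often two share a household is not given. The same boroughs appear in both periods and at all ages, so stable borough differences largely cancel. Young people and other members of their household sit on opposite sides of the contrast, so positive correlation between them partly reduces its variance. Borough-clustered errors therefore do not by themselves imply a particular inflation.

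A shortfall in the deprived-quartile example (stated as 90% for a 15% bus change) might also be inferred. That would rest on 750 people per period, which the protocol does not state. At 750 a simple before-after test gives 86.6%; a quarter of the available sample (about 1,362 v 952) gives 96%.

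None of this makes the stated 80% the power of the planned analysis.

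**Conclusion.** The point holds as a mismatch between the power statement and the planned analysis. The 80% and 98% are correct arithmetic for independent before-after samples of 3,000. For the planned contrast at that size, walking reaches at most about 77.6%, and less with any design effect above 1. Whether the study itself has 80% for walking cannot be settled from the protocol: probably yes for the pooled 12-17 group if the 2008 data are used and clustering is mild, less securely with LTDS 2005-2007 alone. For the separate age bands, a 10% walking change falls short of 80% even with no clustering. The bus figure is not in question in any practical sense.

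These results assume that the 2001 age share persists, that SDs are equal across ages, and that all LTDS respondents count as post-intervention. They also take the Table 2 SDs at face value. That table labels them per trip, while the power statement speaks of daily distance, so the percentages are conditional on those SDs applying to the daily outcome.

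**What to change.** Restate walking and bus power, or the smallest detectable change, for the change-on-change contrast. Give the expected numbers before and after, say whether LTDS 2008 is included, and name the comparator ages. Estimate a design effect for that contrast from LATS 2001, already the source of Table 2, allowing for household and borough. Report the result for ages 12-15 and 16-17 as well as pooled. The original example can stay if it is labelled as a simple before-after comparison of independent individuals.

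The cost is a short recalculation and possibly a less favourable stated figure. Neither the sample nor the analysis needs to change.

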13.1 Summary Timetable

	Year 1: 2010/11				Year 2: 2011/12				Year 3: 2012						
	$^{\rm M}/_{\rm A}$	M/J	J_A	s/o	N_D	J/ _F	$^{\rm M}/_{\rm A}$	M/J	J_A	s/o	N/ _D	J/ _F	$^{\rm M}/_{\rm A}$	M/J	J_A
Recruitment / ethics															
approval															
Update literature review															
Access and prepare															
quantitative data sets															
Review of additional															İ
data sources															
Quantitative analysis															•
Recruit participants															
Qualitative fieldwork															
Qualitative analysis															
Develop economic															
evaluation methodology															
Complete economic															
evaluation															
Seminars-Collaborators															
Workshops/conferences															
Writing up															

13.2 Key Milestones

Year 1

Complete ethical approval	June 2010
First investigators' seminar –develop conceptual model	April 2010
 Access required data sets for quantitative components 	Aug 2010
 Complete review of additional data sets 	Feb 2011
Year 2Complete interviews and focus groups	Aug 2011

		- 3 -
•	Complete qualitative analysis	Oct 2011
•	Complete quantitative analysis	Aug 2011
•	Circulate working paper on casual pathways	Sept 2011
•	Complete economic evaluation	Feb 2012

Year 3

Hold workshop for stakeholders	May 2012
Complete draft papers on empirical findings, implications for	
public health, economic evaluation, methodology	July 2012
Final report to funders	Aug 2012
	Complete draft papers on empirical findings, implications for public health, economic evaluation, methodology

14. Expertise

This proposal arises from the ongoing work at LSHTM and IoE on transport and health, on methods to evaluate public health interventions, on understanding complex interventions, and on direct work with children and young people, and from the ITS at Leeds on the evaluation of transport policy. The research team has a proven track record, with peer-reviewed output in areas including: secondary analysis of transport and health data; the evaluation of complex interventions (including transport interventions); qualitative research with young people and on the use and synthesis of mixed-methods in public health research. Recent and ongoing grants from DH and TfL have included studies of inequalities in road injury, from ESRC on methodological work, from the Canadian Institutes for Health Research on complex interventions, and from WHO on the injuries report for the Commission on the Social

Determinants of Health. Members of the team have collaborated successfully on a large number of previous grants and publications, completed to time and to budget, and have engaged in knowledge translation through scientific and stakeholder publications and engagement with policy makers, end point users of services and practitioners.

The applicants benefit from the institutional base of large multi-disciplinary departments of Public Health at LSHTM, social science at IOE, and the Institute for Transport Studies at Leeds, one of the world's leading academic centres of transport research. The team have excellent links with relevant stakeholders (including TfL, DfT, and the Wellcome convened workshop on Environmental Determinants of Physical Activity). The Transport and Health group at LSHTM is a collaboration that has developed considerable experience of working together on mixed methods studies, and draws on expertise more broadly across LSHTM, and ITS at Leeds has an internationally recognised record of collaborative work on transport policy and appraisal.

15. Members of the public

This study is likely to be of direct interest to the public, not only in London, but also those in cities worldwide who are following with interest the ways in which transport policies in London impact on health, social cohesion, congestion and air quality. Our policy (and practice to date) is to share information in a timely manner. We will do this through briefings to colleagues in TfL, the establishment of an 'On the buses' website which will link to internet networking sites, and short items in mainstream news services generated by young people (http://www.headliners.org/). Young people's input will aid in identifying dissemination opportunities.

Apart from peer-reviewed journal articles on public health, economic evaluation and methodological findings, this research is likely to generate findings useful for policy makers, in particular identifying the range of positive and negative impacts which need to be taken into account when planning new transport policies. This work is therefore likely to be of value in future health impact assessments of transport interventions, including modeling work on likely health impact. In the shorter term, we will ensure that learning in both directions (policy and practice to research and vice versa) will be facilitated through the advisory group, including key stakeholders (London Health Commission representatives, a young people's participation worker; TfL representatives) in a process of integrated knowledge exchange, recognizing the importance of stakeholders to the process of knowledge production. We will publish in stakeholder publications, including those aimed at transport policy makers and public health practitioners. [name] and [name] are part of an international collaboration on complex interventions funded by the Canadian Institutes for Health Research, which provides an opportunity to disseminate the methodological work internationally.

17. References

 - project assessment, Deliverable 2, HEATCO Project. Stuttgart: IER.

- Crum A, Langer E (2007) Mind set matters: exercise and the placebo effect. *Psych Sci* 178: 165-171
- (DoH) Department of Health (2004) Choosing health: making healthier choices easier.
- DfT (1999) Young people and crime on public transport London: DfT
